11.3.2 Statistical Methods

The baseline value for clinical laboratory tests will be the last non-missing measurement on or before the day of the first dose of study drug. Values on Day 1 must also be before the time of first dose if time is available. The same baseline value will be used for change to Treatment Period visits and change to Post-Treatment Period visits.

Mean changes from baseline to each post-baseline visit, including applicable post treatment visits, will be summarized for each age group and overall. Each protocol-specified laboratory parameter will be summarized with the sample size, baseline mean, visit mean, change from baseline mean, standard deviation, minimum, median, and maximum.

The laboratory parameters defined in [Table 15](#) will be assigned a toxicity grade of 1, 2, 3, or 4. The number and percentage of subjects with a maximum toxicity grade of 1, 2, 3 or 4 will be summarized for each age group and overall. To be counted, the post-baseline value must have a toxicity grade that is more extreme than the toxicity grade corresponding to the baseline value. The summary will also include the number and percentage of subjects with a maximum of at least Grade 3 for all laboratory parameters in

Table 15. A listing of all relevant laboratory parameters will be provided for each subject who had an increase to Grade 2 or higher for all laboratory variables in Table 15.

Table 15. Definitions of Toxicity Grades 1, 2, 3, and 4 for Laboratory Values

Test	Grade 1	Grade 2	Grade 3	Grade 4
ALT	> ULN – 3 × ULN	> 3 – 5 × ULN	> 5 – 20 × ULN	> 20 × ULN
AST	> ULN – 3 × ULN	> 3 – 5 × ULN	> 5 – 20 × ULN	> 20 × ULN
Alkaline Phosphatase	> ULN – 2.5 × ULN	> 2.5 – 5 × ULN	> 5 – 20 × ULN	> 20 × ULN
GGT	> ULN – 2.5 × ULN	> 2.5 – 5 × ULN	> 5 – 20 × ULN	> 20 × ULN
Total Bilirubin	> ULN – 1.5 × ULN	> 1.5 – 3 × ULN	> 3 – 10 × ULN	> 10 × ULN
Hemoglobin	< LLN – 100 g/L	< 100 – 80 g/L	< 80 g/L	--
White blood cells	< LLN – 3.0 × 10 ⁹ /L	< 3.0 – 2.0 × 10 ⁹ /L	< 2.0 – 1.0 × 10 ⁹ /L	< 1.0 × 10 ⁹ /L
Absolute Neutrophil Count	< LLN – 1.5 × 10 ⁹ /L	< 1.5 – 1.0 × 10 ⁹ /L	< 1.0 – 0.5 × 10 ⁹ /L	< 0.5 × 10 ⁹ /L
Platelet count	< LLN – 75.0 × 10 ⁹ /L	< 75.0 – 50.0 × 10 ⁹ /L	< 50.0 – 25.0 × 10 ⁹ /L	< 25.0 × 10 ⁹ /L
INR	> 1 – 1.5 × ULN	> 1.5 – 2.5 × ULN	> 2.5 × ULN	--
Glucose (increased)	> ULN – 8.9 mmol/L	> 8.9 – 13.9 mmol/L	> 13.9 – 27.8 mmol/L	> 27.8 mmol/L
Glucose (decreased)	< LLN – 3.0 mmol/L	< 3.0 – 2.2 mmol/L	< 2.2 – 1.7 mmol/L	< 1.7 mmol/L
Creatinine	> ULN – 1.5 × ULN	> 1.5 – 3 × ULN	> 3 – 6 × ULN	> 6 × ULN
Creatinine clearance	< LLN – 60 mL/min	< 60 – 30 mL/min	< 30 – 15 mL/min	< 15 mL/min
Albumin	< LLN – 30 g/L	< 30 – 20 g/L	< 20 g/L	--

Assessment of Hepatic Laboratory Values

The number and percentage of subjects in each age group and overall meeting the following criteria during treatment will be summarized:

- Post nadir (preceding value is lower than the subsequent value)
ALT > 5 × ULN (regardless of grade change);
- Total bilirubin ≥ 2 × ULN and > baseline (i.e., a post-baseline value must be more extreme than the baseline value to be considered)
- Post nadir ALT > 3 × ULN and total bilirubin > 2 × ULN (Hy's law quadrant)

- Post nadir ALT > 3 × ULN and total bilirubin ≤ 2 × ULN (Temple's corollary quadrant)

Four listings (one for each bullet above) of all liver function tests including ALT, AST, total, indirect and direct bilirubin, ratio of direct to total bilirubin, and alkaline phosphatase values will be provided for each subject who met the criterion defined above.

Hepatic Laboratory Abnormalities of Interest

Among the labs assessed under "Assessment of Hepatic Laboratory Values" the following criteria are of interest:

- Confirmed post-nadir ALT > 5 × ULN;
- Post nadir ALT > 3 × ULN and a concurrent total bilirubin > 2 × ULN with direct bilirubin/total bilirubin ratio > 0.4

Two listings (one for each bullet) of all liver function tests including ALT, AST, total, indirect and direct bilirubin, ratio of direct to total bilirubin, and alkaline phosphatase values will be provided for each subject who met the criterion defined above.

For the **assessments of hepatic laboratory values** and **hepatic laboratory abnormalities of potential interest**, the maximum ratio relative to the ULN will be used to determine if subjects meet any of the criteria listed above. The ALT and total bilirubin values do not need to be concurrent in order to meet the defined criteria in statistical summaries. For ALT, the post-baseline value must represent an increase from the first nadir (including baseline) to be counted. First nadir is defined as the last value prior to the first increase. For total bilirubin, a subject will be counted if the post-baseline laboratory value meets the above criteria regardless of the baseline laboratory value (i.e., the post-baseline laboratory value does not need to be worse than the baseline laboratory value), except where noted above. A confirmed post-nadir increase in ALT is defined as two consecutive values of ALT > 5 × ULN after nadir, either both during treatment or at the final treatment measurement and the next consecutive post-treatment measurement. A single post-nadir ALT value of greater than 5 × ULN followed by lost to

follow-up (no additional ALT values) also will be considered (i.e., will not require confirmation). The ratio of direct to total bilirubin will be calculated using the same date/time sample corresponding to the total bilirubin elevation.

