### **6.1.7.2 Management of ALT Elevations**

If the ALT increase is confirmed to be  $> 5 \times \text{ULN}$  which is also  $> 2 \times$  baseline value, the recommendations below should be followed:

- Evaluate for alternate etiology of ALT elevation; document in the source, update the medical history and concomitant medications eCRF (if applicable), and obtain additional testing as appropriate.
- Evaluate for a new viral hepatitis infection, including hepatitis A, B and E.
  - If the subject is found to have an active hepatitis B infection, additional evaluation by completion of the eCRF Transaminase Elevations Questionnaire should be performed by the investigator.

- Manage the subject as medically appropriate.
- Repeat ALT, AST, total and fractionated bilirubin, alkaline phosphatase and international normalized ratio (INR) within 1 week. Repeat liver chemistries as indicated until resolution.
- Discontinue study drugs if any of the following is observed at any time:
  - ALT level is  $\geq 20 \times$  ULN in the absence of an alternate etiology.
  - Increasing direct bilirubin or INR or onset of symptoms/signs of hepatitis.
  - At the discretion of the investigator.

Alternate management of ALT increases is permitted with approval of the Primary Therapeutic Area Medical Director.

If the investigator wishes to pursue alternative management of study drugs in the setting of confirmed ALT increases described above, then approval of the Primary Therapeutic Area Medical Director must be obtained.

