6.1.2 Study Days

Study days are calculated for each time point relative to the first dose of study drug. Study days are negative values when the time point of interest is prior to the first study drug dose day. Study days are positive values when the time point of interest is after the first study drug dose day. There is no Study Day 0. Study Day 1 is the day of the first dose of study drug.

Study Drug End Days (Days Relative to the Last Dose of Study Drug)

Study drug end days are calculated for each time point relative to the last dose of study drug. The last day of study drug dosing is defined as Study Drug End Day 0. Days before it have negative study drug end days and days after it have positive study drug end days.

Final Treatment Value

The final treatment value is defined as the last non-missing measurement collected after Study Day 1 and on or before Study Drug End Day 2.

Final Post-Treatment Value

The final post-treatment value for each subject is the last non-missing measurement collected after Study Drug End Day 2 and on or before Study Drug End Day 1,999.

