b. For 12-week treatment only.

c. For 16-week treatment only.

d. The last value within the window will be used to define the Final Treatment Visit value. The upper bound of this Final window is Study Drug End Day ≤ 2.

Note: Data must also have Study Drug End Day ≤ 2 for all windows. The result closest to the scheduled time point will be used.

Table 4. Analysis Time Windows for HCV RNA and Resistance Endpoints (Post-Treatment Period)

Scheduled Visit ^a	Nominal Day (Study Drug End Day)	Time Window (Study Drug End Day Range)
Post-Treatment Week 4	28	3 to 56
Post-Treatment Week 12	84	57 to 126
Post-Treatment Week 24	168	127 to 210
Post-Treatment Week 36	252	211 to 294
Post-Treatment Week 48	336	295 to 504
Post-Treatment Week 96	672	505 to 840
Post-Treatment Week 144	1,008	841 to 1,999
SVR ₄ ^b	28	3 to 56
SVR ₁₂ ^b	84	57 to 126
SVR ₂₄ ^b	168	127 to 210

a. Post-Treatment Visits are applicable to subjects who received at least one dose of study drug.

b. For SVR windows, the last value in the window will be used.

Note: The result closest to the scheduled time point will be used, except for SVR₄, SVR₁₂, and SVR₂₄. Data must also have Study Drug End Day > 2 for all windows. Study Drug End Day 0 is defined as the day of the last dose of study drug.

Table 5. Laboratory Data, Vital Sign Measurements, Growth and Development Endpoints (Except Growth Rate) Visit Windows (Post-Treatment Period)

Scheduled Time	Nominal Day (Study Drug End Day)	Time Window (Study Drug End Days Range)
Post-Treatment Week 4	28	3 to 42
Post-Treatment Week 12	84	71 to 126
Post-Treatment Week 24	168	127 to 210
Post-Treatment Week 36	252	211 to 294
Post-Treatment Week 48	336	295 to 504
Post-Treatment Week 96	672	505 to 840
Post-Treatment Week 144	1,008	841 to 1,999
Final Post-Treatment Visit ^a	> 2 days after the last dose of study drug	

a. The last value within the Post-Treatment Period window will be used to define the final post-treatment value. The lower bound of this Final window is Study Drug End Day 3.

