11.2.1 Treatment-Emergent Adverse Events

Treatment-emergent AEs are defined as any adverse event with an onset date that is after the first dose of study drug and no more than 30 days after the last dose of study drug. Events where the onset date is the same as the study drug start date are assumed to be treatment-emergent. If an incomplete onset date was collected for an adverse event, the event will be assumed to be treatment-emergent, unless there is other evidence that confirms that the event was not treatment-emergent (e.g., the event end date was prior to the study drug start date).

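### SAP 11.3.2 counts its liver criteria only on treatment, so a child whose bilirubin crosses 2 × ULN after the drug is stopped is tabulated under Temple's corollary, not Hy's law

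*SAP*

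**What the plan says.** SAP 11.3.2 (Assessment of Hepatic Laboratory Values) introduces four criteria with "The number and percentage of subjects in each age group and overall meeting the following criteria during treatment will be summarized". The four are post-nadir ALT above 5 × ULN; total bilirubin at least 2 × ULN and above baseline; the Hy's law quadrant (post-nadir ALT above 3 × ULN with total bilirubin above 2 × ULN); and the Temple's corollary quadrant (the same ALT limit with total bilirubin at or below 2 × ULN). Two further abnormalities of interest are drawn from the same laboratory values. Each subject is classified on the maximum ratio to ULN, and ALT and bilirubin need not be concurrent.

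The section does not say when the treatment period ends. Elsewhere:

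- The note to SAP Table 3, which sets the treatment-period laboratory windows, says "Data must also have Study Drug End Day ≤ 2 for all windows".
- SAP 6.1.2 defines the final treatment value as the "last non-missing measurement collected after Study Day 1 and on or before Study Drug End Day 2".
- Protocol 1.3 (Definition of Terms) ends the Treatment Period at the last dose.
- SAP 11.2.1 takes adverse events as treatment-emergent if onset is "no more than 30 days after the last dose of study drug".

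Protocol 6.1.7.2 applies once ALT is confirmed above 5 × ULN and above twice baseline. One of its listed reasons for discontinuing study drug is "Increasing direct bilirubin or INR or onset of symptoms/signs of hepatitis". It asks for liver tests to be repeated within a week, and then "Repeat liver chemistries as indicated until resolution".

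**The concern.** The protocol's own liver rule can end treatment while bilirubin is rising but has not yet reached 2 × ULN. Ending treatment also closes the SAP's counting period. A later bilirubin value, obtained from the repeat tests that the protocol requests, then cannot move the child into the Hy's law count. Because the on-treatment ALT already qualifies, the child is placed in the milder quadrant instead of simply being left out.

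The SAP recognises that liver values after the last dose can matter. A confirmed ALT rise above 5 × ULN may use the next post-treatment measurement. There is no equivalent for bilirubin or for the paired criteria. Safety by age group is a primary objective (Protocol 4.1), so the paired liver counts should mean what a reader will take them to mean.

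**Working it through.** The plan states no figure for this point, so there is none to reproduce. The check is of the counting rule.

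**Step 1: where the periods end.** Hepatic criteria end at Study Drug End Day 2 (SAP Table 3 and 6.1.2), or End Day 0 on the protocol's definition. Treatment-emergent adverse events end at End Day 30. The gap is 30 − 2 = 28 days (End Days 3 to 30). The first post-treatment laboratory window covers End Days 3 to 42 (SAP Table 5), so values in the gap are collected and assigned to a visit.

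**Step 2: apply the rule to an assumed child.** These values are illustrative and not from the documents (multiples of ULN):

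| Study Drug End Day | ALT | Total bilirubin |
|---|---|---|
| −28 | 0.8 | 0.6 |
| 0 | 6.0 | 1.6 |
| 7 | 8.0 | 2.8 |
| 28 | 2.0 | 1.2 |

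Taking the maximum of each test up to the cut-off:

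| Cut-off (End Day) | Max ALT | Max bilirubin | Hy's law | Temple's corollary | Bilirubin ≥ 2 × ULN |
|---|---|---|---|---|---|
| 0 or 2 | 6.0 | 1.6 | no | yes | no |
| 30 or 42 | 8.0 | 2.8 | yes | no | yes |

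The result is the same at End Day 0 and End Day 2, so it does not depend on which definition of treatment is used.

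**Step 3: a child whose ALT first exceeds 3 × ULN at Post-Treatment Week 4** (nominal End Day 28). No on-treatment ALT qualifies, so neither quadrant nor the ALT criterion is met. Unless on-treatment bilirubin qualified by itself, the child enters none of the four counts.

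**Step 4: scheduled panels affected.** Protocol Appendix C gives 3 post-baseline on-treatment chemistry panels for 8 weeks of treatment (Weeks 2 and 4, end of treatment), 4 for 12 weeks and 5 for 16 weeks. Adding Post-Treatment Week 4, the share left out is 1/4 = 25%, 1/5 = 20% and 1/6 = 17%. Repeat tests after stopping come on top. These are shares of panels for children who complete treatment, not shares of cases.

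**Step 5: effect of one reclassified child.** The plan specifies no interval for these counts; Wilson's 95% interval is used here for illustration. With p = x/n and z = 1.96, the limits are [p + z²/2n ± z√(p(1−p)/n + z²/4n²)] / (1 + z²/n). For x = 0 the upper limit reduces to z²/(n + z²), which is 3.84/128.84 = 2.98% for n = 125. The denominators are the protocol's planned total and its target of about 22 per Part 2 age group at the final dose.

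| n | 0 cases (95% CI) | 1 case (95% CI) |
|---|---|---|
| 125 | 0% (0 to 2.98%) | 0.8% (0.14 to 4.39%) |
| 22 | 0% (0 to 14.9%) | 4.5% (0.8 to 21.8%) |

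**The case against.** The strongest reply is that the child stays visible, and much of it stands.

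- **Adverse events.** Protocol 6.1.1.1 treats a laboratory abnormality as an adverse event when it meets the toxicity-management criteria. A child stopped under 6.1.7.2 should therefore appear among events leading to discontinuation, and events are collected to 30 days.
- **Hepatic listings.** A child with qualifying on-treatment ALT enters the corresponding listings in 11.3.2. These show all liver function tests, with no stated date limit.
- **Grade 2 listing.** The SAP's listing for any increase to Grade 2 or higher includes ALT above 3 × ULN and sets no on-treatment limit. It could show a first rise at Post-Treatment Week 4. (Protocol 8.1.5.2 does restrict its toxicity-grade summary to treatment, so this depends on the SAP text.)
- **Discontinuation visit.** A chemistry panel is due no later than 2 days after the final dose (Protocol 5.4.1, Appendix C), inside the counting period. The gap is then limited to children still at or below 2 × ULN at that visit.
- **Convention.** An on-treatment laboratory summary matches the protocol's own practice and keeps out ALT rises caused by relapse.

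A reader might go further and infer that the case disappears, or that one misplaced child would overturn the liver-safety conclusion. The documents do not support either. The routes above preserve the case, and the SAP also reports hepatic adverse events of special interest. Protocol 3.0 reports no adult cases consistent with drug-induced liver injury. Of the four adults described there, three had ALT abnormalities that were not clinically significant, and the one with paired elevations had gallstones.

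None of these routes corrects the tabulated Hy's law count or the quadrant. Dropping the need for concurrency loosens the pairing of values but does not lengthen the period.

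**Conclusion.** The point holds as a defect in tabulation. All four hepatic criteria stop with treatment. A bilirubin value first above 2 × ULN on Study Drug End Day 3 or later leaves a child with qualifying on-treatment ALT under Temple's corollary, and ALT first above 3 × ULN at Post-Treatment Week 4 is not counted. A child already above both limits by End Day 2 is counted correctly.

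The End Day 2 limit is inferred from the SAP's windows and its final treatment value, because 11.3.2 leaves the phrase undefined. The protocol's definition is stricter, so the conclusion does not rest on that inference. The documents give no event rate, so the expected number of affected children is unknown and may be zero. The effect of one case is as in the table. The change is worth making because the data are already collected and the counts serve a primary safety objective.

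**What to change.** In SAP 11.3.2:

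1. Define the counting period. Report the four hepatic criteria and the two abnormalities of interest from first dose through 30 days after the last dose, matching SAP 11.2.1.
2. Also include the scheduled Post-Treatment Week 4 panel when it is drawn after day 30 but within its Table 5 window (to End Day 42).
3. Keep the on-treatment count (Study Drug End Day 2 or earlier) as a sub-row.
4. Flag any case first met off drug with HCV RNA at or above LLOQ. Appendix C schedules HCV RNA at Post-Treatment Week 4; for an unscheduled repeat, use the nearest sample.

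The cost is SAP wording, one extra row per table and a flag, with no new visits or samples. The downside is that a few relapse-related ALT rises may enter the wider count; the flag and the sub-row identify them. No change to any stopping rule or other clinical management is proposed.

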11.4 Analysis of Vital Signs and Weight

11.4.1 Variables and Criteria Defining Abnormality

Vital sign variables measured are body temperature, sitting systolic blood pressure, sitting diastolic blood pressure, sitting pulse rate, body weight, height, and BMI.

11.4.2 Statistical Methods

The baseline value for vital signs will be the last measurement on or before the day of the first dose of study drug. The same baseline value will be used for change to Treatment Period visits and change to Post-Treatment Period visits.

Changes from baseline to each post-baseline visit, including applicable post-treatment visits, will be summarized for each age group and overall. Each vital sign parameter will be summarized with the baseline mean, visit mean, change from baseline mean, standard deviation, minimum, median, and maximum.

12.0 Summary of Changes

12.1 Summary of Changes Between the Latest Version of the Protocol and SAP Version 1.0

1. The protocol stated to use Safety Population for Demog/baseline outputs; SAP changed these analyses to be run on ITT to align with the new HCV SAP template.
2. Protocol Section 8.1.6.2 planned shift tables for clinical laboratory values from low/normal to high and high/normal to low; SAP removed these analyses as the reference ranges won't work for the pediatric population.

3. Protocol Section 8.1.6.3 planned summary table for vital signs meeting Potentially Clinically Significant criteria; SAP removed these analyses due to the criteria are not applicable to pediatric population.
4. Protocol Section 8.1.3 planned change from baseline summary statistics for height, weight, and BMI z scores; SAP removed these analyses as the summary of the z scores at each applicable visit is sufficient.
5. Updates were made to the subgroup efficacy analysis section to be consistent across the HCV glecaprevir/pibrentasvir program.

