#### **8.1.3 Growth and Development**

The following growth and development endpoints will be calculated in the ITT population.

- Growth rate at Post-Treatment Weeks 12, 48, 96 and 144 (defined as change in height over change in age from the previous visit)
- Weight z score
- Height z score
- Body mass index (BMI) z score

Growth rate will be summarized with N, mean and SD together, median and range together at each applicable post baseline visit by gender for all and for age group separately. Weight, height and BMI z scores will be summarized with N, mean and SD together, median and range together at each applicable post baseline visit for all and by age group. Change from baseline in weight and height will be summarized together with other vital signs such as temperature and blood pressure.

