3.0 Introduction

This statistical analysis plan (SAP) describes the statistical analyses to be completed by the AbbVie Statistics and Statistical Programming Departments, or designee, for Study M16-123.

Study M16-123 assesses the pharmacokinetics, safety, and efficacy of glecaprevir/pibrentasvir (GLE/PIB) in pediatric subjects with chronic hepatitis C virus (HCV) genotypes 1 – 6 chronic Infection with or without compensated cirrhosis and with or without HIV infection, who are HCV treatment-naïve or interferon/pegylated interferon (IFN), ribavirin (RBV) and/or sofosbuvir (SOF) treatment-experienced subjects.

This SAP (Version 1.0) provides details to further elaborate the statistical methods outlined in Clinical Study Protocol M16-123 Amendment 1 dated 25 July 2017, and describes analysis conventions to guide the statistical programming. Analyses will be performed using SAS[®] Version 9.4 (SAS Institute, Inc., Cary, NC) or later under the UNIX operating system.

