7.1 Demographic and Baseline Characteristics

Categorical demographic and baseline characteristic variables will be summarized with the number and percentage of subjects. Continuous variables will be summarized with descriptive statistics (number of non-missing observations, mean, standard deviation, median, maximum and minimum).

Continuous demographic variables include age, weight, height, and body mass index (BMI), BMI z score (BMI z score will be calculated using WHO published BMI-for-age z score tables),⁵ weight and height z scores (weight and height z scores will be calculated using WHO published weight-for-age z score and height-for-age z score tables).

Categorical demographic variables include sex, race, black race (black or non-black), ethnicity, age category (≥ 3 to < 6 years, ≥ 6 to < 9 years, ≥ 9 to < 12 years, ≥ 12 to < 18 years), birth year, weight category (≥ 12 to < 20 kg, ≥ 20 to < 30 kg, ≥ 30 to < 45 kg, ≥ 45 kg), weight z score category (< -1 , -1 to 1 , > 1), Height z-score category (< -1 , -1 to 1 , > 1), BMI z-score category (< -1 , -1 to 1 , > 1) country, and geographic region (North America, Europe, or Japan).

Weight-for-age reference data are not available beyond age 10 because this indicator does not distinguish between height and body mass in an age period where many children are experiencing the pubertal growth spurt and may appear as having excess weight (by weight-for-age) when in fact they are just tall. Subjects who are older than 10 years at the time of the corresponding weight measurement will be excluded from the summary of weight z score.

When defining geographic region, sites in the United States, Puerto Rico, and Canada will be grouped under North America; sites in Belgium, Germany, Russia, Spain and the United Kingdom will be grouped under Europe; sites in Japan will be grouped together as Japan.

Continuous baseline characteristics include baseline \log_{10} HCV RNA level, creatinine clearance, eGFR, platelet count, albumin, GGT, alpha fetoprotein (for cirrhotic subjects only), Fibrotest, APRI, FIB-4, AST, ALT, total, direct, and indirect bilirubin for all subjects.

Categorical baseline characteristics include:

- HCV genotype and subtype (using central laboratory results and final genotype/subtype results, see Section 10.8);
- Prior HCV treatment history (naïve or experienced);
- For treatment-experienced subjects, type of previous regimen (IFN- or SOF-based);

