10.9 Growth and Development

The following growth and development endpoints will be calculated in the ITT population.

- Growth rate at Post-Treatment Weeks 12, 48, 96 and 144 (defined as change in height over change in age from the previous visit)
- Weight z score⁵
- Height z score⁵
- Body mass index (BMI) z score⁵

Weight, height, and BMI z scores will be calculated using WHO published weight-for-age z score, height-for-age z score, and BMI-for-age z score tables, respectively. As described in Section 7.1, subjects who are older than 10 years at the time of the corresponding weight measurement will be excluded from the analyses of weight z score. If a subject becomes older than 19 years during the study, the WHO standards at 19 years old will be used to calculate height z score and BMI z score after 19 years old as these WHO standards are very close to the adult standards.

Growth rate will be summarized with N, mean and SD together, median and range together at each applicable post baseline visit by gender for all and for age group separately. Weight, height and BMI z scores will be summarized with N, mean and SD together, median and range together at each applicable post baseline visit for all and by age group.

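### Weight z-score is summarised by visit only, with measurements after age 10 excluded, so in the 6 to <9 and 9 to <12 groups and the overall row the mean can drift with no child changing

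*SAP*

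**What the plan says.** SAP 10.9 plans descriptive statistics at each post-baseline visit, overall and by age group: "Weight, height and BMI z scores will be summarized with N, mean and SD together", plus median and range. For weight only, children "older than 10 years at the time of the corresponding weight measurement will be excluded from the analyses of weight z score". SAP 7.1 applies the same rule at baseline, where such children "will be excluded from the summary of weight z score", and explains that no weight-for-age reference exists beyond that age. Height and BMI z-scores continue: "the WHO standards at 19 years old will be used to calculate height z score and BMI z score after 19 years old".

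SAP 12.1, item 4, records what was dropped: "Protocol Section 8.1.3 planned change from baseline summary statistics for height, weight, and BMI z scores". It then gives the reason: "SAP removed these analyses as the summary of the z scores at each applicable visit is sufficient". The SAP was written against "Clinical Study Protocol M16-123 Amendment 1 dated 25 July 2017". Section 8.1.3 of the current protocol also plans z-scores by visit only. It keeps change for raw values: "Change from baseline in weight and height will be summarized together with other vital signs such as temperature and blood pressure".

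Two within-child analyses remain in the SAP. Section 11.4.2 gives change from baseline in the vital signs, which include raw weight, height and BMI. Table 6 and Section 10.9 give growth rate, the change in height per year of age since the previous visit.

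**The concern.** The study has no control arm, so a child's own baseline is the only internal comparator for growth. Protocol 5.1.3 names growth and development as something the post-treatment period will assess, and lists weight z-score among the measures.

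The age-10 rule is applied measurement by measurement, so children leave the weight z summary as they age. A reader who compares the baseline mean with the PT Week 144 mean is then comparing different sets of children. A fall could be read as poor weight gain, and a rise as catch-up, when neither occurred. The retained analyses do not settle the question. Raw weight and height are expected to increase in growing children, and neither the raw changes nor the growth rate is standardised for age.

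**Working it through.** The documents give no size or precision figure for growth, so there is no stated figure to reproduce.

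**Inputs from the documents.** Part 2 groups are 3 to <6, 6 to <9 and 9 to <12 years, with about 81 children in total (Protocol 5.1). Treatment lasts 8, 12 or 16 weeks, and follow-up runs to PT Week 144. The age-10 rule is in SAP 7.1 and 10.9.

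**Assumptions, not in the documents.** Ages are uniform within group, there are 81/3 = 27 children per group, treatment lasts 8 weeks, visits are at nominal times and there is no dropout.

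**Step 1: share still aged 10 or younger.** Share = (10 − t − lower age)/3, limited to 0 to 1, with t = (8 + PT weeks)/52.18 years.

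| Visit | t (years) | 6 to <9 | 9 to <12 |
|---|---|---|---|
| Baseline | 0 | 100% | (10 − 9)/3 = 33% |
| PT Week 12 | 20/52.18 = 0.38 | 100% | 0.62/3 = 21% |
| PT Week 48 | 56/52.18 = 1.07 | 2.93/3 = 98% | 0% |
| PT Week 96 | 104/52.18 = 1.99 | 2.01/3 = 67% | 0% |
| PT Week 144 | 152/52.18 = 2.91 | 1.09/3 = 36% | 0% |

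With 16 weeks of treatment, the 6 to <9 share at PT Week 144 is (10 − 160/52.18 − 6)/3 = 31%. In the 3 to <6 group, a child enrolled just under 6 is about 6 + 2.91 = 8.9 years old at PT Week 144, so none leave. The 12 to <18 group never has a weight z-score.

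**Step 2: number in the overall row.** Baseline 27 + 27 + 9 = 63; PT Week 48, 27 + 26.3 = about 53; PT Week 96, 27 + 18 = 45; PT Week 144, 27 + 9.8 = about 37.

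**Step 3: drift when every child's z is constant.** Suppose z varies with baseline age by b per year. The expected shift is b × (mean baseline age of those remaining − mean baseline age of those summarised at baseline).

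- 6 to <9 group: those remaining at PT Week 144 were 6 to 7.09 at entry, mean 6.54, against 7.5. The shift is −0.96b, or −0.10 for b = 0.1 and −0.19 for b = 0.2.
- Overall row: the baseline mean age is (27 × 4.5 + 27 × 7.5 + 9 × 9.5)/63 = 6.50. At PT Week 144 it is (27 × 4.5 + 9.8 × 6.54)/36.8 = 5.04. The shift is −1.46b, or −0.15 for b = 0.1, −0.29 for b = 0.2 and +0.15 for b = −0.1.

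**Step 4: chance drift when z is unrelated to age.** A simulation of 20,000 trials with constant z per child and SD 1 (also assumed) gave an expected shift of 0. In the 6 to <9 group at PT Week 144 the SD of the shift was 0.27 with 27 children and 0.30 with 22. The mean moved by more than 0.2 in 44% to 48% of trials. In the overall row the SD was 0.11 to 0.12.

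**Step 5: the paired alternative.** Within-child change is exactly zero at every visit in the same simulation, because each child's z is constant by construction.

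**The case against.** Much of the case for leaving the SAP alone stands:

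- The exclusion is justified, because no weight-for-age reference exists beyond age 10. BMI z gives an age-standardised body-mass measure for older children.
- N is shown at each visit and results are given by age group, so the shrinking set is visible. It is not corrected, however.
- Growth rate is a within-child look at height, and the raw change tables report a minimum, so a child who lost weight or gained none could show up.
- Growth is not a listed primary or secondary objective in Protocol 4.1 or 4.2.

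A reader might infer several stronger things that the documents do not support:

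- That all three z-scores are affected. Height and BMI z have no age-10 cut, so their sets change only through missed visits or dropout.
- That the SAP departs from the current protocol. Section 8.1.3 now plans visit summaries only, and item 4 of SAP 12.1 describes an earlier version.
- That the drift has a known direction. Its sign follows the assumed age slope.
- That unpaired means cost precision in a planned inference. No standard error, interval or test of growth change is planned.

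**Conclusion.** The point holds for weight z-score in the 6 to <9 group (mainly PT Weeks 96 and 144), the 9 to <12 group before PT Week 48, and the overall row. In those places a change in mean weight z cannot be separated from older children leaving the set, so the visit summary is not sufficient on its own.

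The attrition shares rest on uniform ages and 8 weeks of treatment, and the counts also on 27 per group. Under those assumptions the loss is substantial: about two thirds of the 6 to <9 group by PT Week 144. The size and sign of any drift are not known. The shifts of −0.29 to +0.15 in the overall row illustrate assumed age slopes of 0.2 to −0.1 per year and are not predictions.

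No retained analysis gives a within-child, age-standardised change for any growth measure. This is a weakness in a descriptive analysis that is cheap to correct. It does not affect the pharmacokinetic, efficacy or main safety conclusions.

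**What to change.** In SAP 10.9:

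- Add, at each post-baseline visit by age group and overall, N, mean, SD, median and range of within-child change from baseline in weight z-score. Use children aged 10 or younger at both measurements, and show the baseline mean of those same children.
- Give the same paired summary for height and BMI z-scores, among children with both values.
- State that weight z-score follow-up is truncated in the 6 to <9 group and absent in the 9 to <12 group from about PT Week 48.
- Keep the visit summaries.

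Leave item 4 of SAP 12.1 as history, or update it to note that the analysis has been reinstated.

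The cost is one extra descriptive table per z-score, from data already collected. The change does not recover children past age 10: at PT Week 144 the paired weight z set in the 6 to <9 group is still only about 36% of those enrolled.
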